### **Proposed statistical analysis for Aim 1: Cartilage healing**

The T1GD value on dGEMRIC measures GAG content in cartilage. Higher T1GD values are associated with higher GAG content in the tissue, a positive measure of cartilage health. We assume that the value is approximately normal.

We plan to fit a general linear mixed model [39] for the outcome of T1GD. Predictors will include the visit at which the T1GD test was performed (initial MRI and 6 months), whether the site was weight bearing or not, and whether the side was affected or not, and the treatment group. Age will be included as a covariate. An unstructured covariance will be used to account for correlation between T1GD measurements on the same participant. Jackknifed-studentized residuals will be examined to assess normality, and transformations will be applied as appropriate.

We will test the null hypothesis of no time by treatment by weight bearing surface by affected side interaction. Given a non-significant interaction, we will test the main effects of time and treatment, comparing the difference between the weight-bearing and non-weight bearing surface for the affected and non-affected sides. Estimates, 95% confidence intervals, and p-values will be produced. All hypothesis tests will be performed using the Wald test with Kenward and Roger degrees of freedom[40] . Hypothesis tests will be performed at the Bonferroni corrected alpha of  $0.05/3 = 0.017$ .

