### **Proposed statistical analysis for Aim 2: Functional Recovery and Symptoms**

We will analyze scores for each subscale of the KOOS-child, and the overall score produced by the pedi-IKDC range from 0 to 100, with higher scores indicating improved knee function. Each measure is approximately normal.

We describe the analysis for Aim 2, Sub-aim 2.1. The analyses for the other sub-aims are exactly parallel.

We plan to fit a general linear mixed model [39] with the pain subscale of the KOOS-child as the outcome. Predictors will include the visit at which the survey was given (6 weeks, 12 weeks, 6 months, 9 months and 12 months) and treatment group. Age will be included as a covariate. An unstructured covariance will be used to account for correlation between measurements on a single participant. If the resulting model fails to converge, a spatial exponential covariance will be used. Jackknifed-studentized residuals will be examined to assess normality, and transformations will be applied as appropriate.

We will test the null hypothesis of no polynomial time trend by treatment interaction. If the time-by-treatment test is non-significant, we will step down to test the main effects of time and treatment. Estimates, 95% confidence intervals, and p-values will be produced.

All hypothesis tests will be performed using the Wald test with Kenward and Roger degrees of freedom [40] . Three hypothesis tests may be performed for each outcome, for a total of 12 tests. To control for multiple comparisons, all hypotheses will be tested at the Bonferroni corrected alpha level of  $0.05/12=0.004$ .

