### **Proposed statistical analysis for Aim 3: Correlation of MR Findings and Measures of Functional Recovery and Symptoms**

We plan to fit four general linear univariate models with 6-month T1GD as the outcome. The primary predictor for each model will be the 6 month measurements of the pain subscale of KOOS-child, the ADL subscale of the KOOS-child, the sports subscale of the KOOS-child, and the pedi-IKDC, respectively. In each model, age will be included as a covariate. We will test the null hypothesis of no association between the functional measure and T1GD findings on MR and/or no decrease in DiPaolo score, using an F test. All hypotheses will be tested at the Bonferroni corrected alpha level of  $0.05/4 = 0.0125$ .

Interim analysis and planned interim power analysis.

Because this study has never been done in children, the estimates for power analysis may be incorrect, and the effect of the treatment may be better or worse than that reported in the literature. Thus, after the first six study participants have been recruited, treated, and followed, the investigators will report blinded data to the study statistician, who will perform an interim power analysis using the methods of Gurka et al., 2007 [41].

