### **Power Analysis**

We conducted a power analysis for Aim 1, the primary endpoint of the study. The maximum sample size for the proposed trial is fixed at 12 patients per arm (24 participants total). The sample size is limited due to costs associated with dGEMRIC.

We calculated power for the test of no difference in T1GD between the treatment groups. We assumed a standard deviation of 50 ms for T1GD values, and a correlation of 0.2 between the baseline MRI and the 12-month T1GD measurements. Estimates were based on T1GD values reported by Neuman et al[42]. We expect T1GD values to be 85 ms higher in the injection group when compared to conservative therapy at the 6 month time point with no difference at baseline. We calculated power for 10, 11, or 12 participants per arm. Power was calculated using GLIMMPSE version 2.0.1.[43]

To detect a mean difference of 85 ms in T1GD between the treatment groups, power will be 0.93 with a Type I error rate of 0.05, for 12 participants per treatment group. To ensure a conclusive study, we will target an effective sample size of 10 participants per group. Over the 12 months, we expect to lose up to two participants per treatment group. To account for the attrition, we have set an enrollment goal of 24 participants, or 12 participants per treatment group.

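### The Aim 3 models pool both arms without a treatment term, so a significant result cannot by itself show that imaging tracks function within arms.

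*Combined protocol and SAP*

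**What the plan says.** The Aim 3 analysis section states: "We plan to fit four general linear univariate models with 6-month T1GD as the outcome". On the predictors it says: "The primary predictor for each model will be the 6 month measurements of the pain subscale of KOOS-child", and it goes on to name the ADL and sports subscales and the pedi-IKDC for the other three models. The adjustment is given in one sentence: "In each model, age will be included as a covariate". The hypothesis is worded: "We will test the null hypothesis of no association between the functional measure and T1GD findings on MR". Each F test is made at 0.05/4 = 0.0125.

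Treatment group is not listed for these models. It is listed for the other two aims: the Aim 1 predictors end with "and whether the side was affected or not, and the treatment group", and the Aim 2 predictors are the visits "6 weeks, 12 weeks, 6 months, 9 months and 12 months) and treatment group".

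Four models and a divisor of four imply one test per functional measure over both arms; separate models per arm would be eight tests. The endpoint line under Aim 3 in Specific Aims speaks of comparing outcomes between the two patient groups. Nothing in the analysis section turns that into a treatment term, an interaction or a stratified analysis.

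**The concern.** The trial hypothesis is that PRP improves both symptoms and imaging appearance. The Power Analysis puts a figure on the imaging side: "We expect T1GD values to be 85 ms higher in the injection group when compared to conservative therapy at the 6 month time point". That is the time point Aim 3 uses. If the hypothesis is right, treatment is a common cause of the two variables being related, and pooling the arms without a treatment term lets the difference between arms appear as an association between imaging and function.

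Patients and parents know the assignment and the functional scores are self-reported. An arm difference in scores is therefore plausible even where cartilage plays no part in it.

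What is at stake is how a positive Aim 3 result is read. Aim 3 would be of most use if it showed that patients with better cartilage values also function better, given the same treatment. The pooled slope mixes that with the fact that one arm may do better on both measures.

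**Working it through.** **Inputs from the documents.**
- Four tests, so 0.05/4 = 0.0125; the plan's figure is reproduced.
- T1GD effect at 6 months 85 ms, with "We assumed a standard deviation of 50 ms for T1GD values, and a correlation of 0.2". Taking 50 ms as the within-arm SD, d1 = 85/50 = 1.7 SD.
- 12 patients per arm enrolled, 10 per arm as the effective size after dropout, 1:1 allocation.

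**Inputs assumed.**
- Functional effect d2 of 0.3, 0.5, 1.0 or 1.5 SD. The documents give no size for it.
- Zero within-arm association between T1GD and function, to isolate what the arm difference alone produces.
- Age unrelated to either outcome.
- 5 per arm as a low case. Under 6 month Research MRIs, only patients whose diagnostic scan was dGEMRIC have dGEMRIC at 6 months, so only they have T1GD. The documents do not say how many that will be.

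**Induced correlation.** With 1:1 arms and zero within-arm correlation,

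r = (d1·d2/4) / √[(1 + d1²/4)(1 + d2²/4)].

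For d1 = 1.7 and d2 = 1.0: the numerator is 1.7 × 1.0/4 = 0.425; the denominator is √(1.7225 × 1.25) = 1.467; r = 0.29.

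**Rejection rate.** The planned model (T1GD on score and age, tested at 0.0125) was simulated with at least 20,000 trials per setting.

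| Functional effect (assumed) | Induced r | 12 per arm | 10 per arm | 5 per arm (assumed) |
|---|---|---|---|---|
| 0.3 SD | 0.10 | 2% | 2% | 2% |
| 0.5 SD | 0.16 | 4% | 3% | 2% |
| 1.0 SD | 0.29 | 12% | 9% | 4% |
| 1.5 SD | 0.39 | 26% | 20% | 7% |

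With treatment group added, all settings return to about 1.0% to 1.5%, against the nominal 1.25%.

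**Sensitivity.**
- If PRP affects T1GD only, or function only, r is zero and the pooled test rejects at about 1.25%.
- With half the planned T1GD effect (0.85 SD) and 12 per arm, rejection is about 1.6% to 8.9% for functional effects of 0.3 to 1.7 SD.

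**Power of the two slopes** (T1GD effect 1.7 SD, assumed within-arm correlation 0.5, 12 per arm, 0.0125).
- Function depends on treatment only through T1GD: 76% pooled, 46% adjusted. With 10 per arm, 64% and 36%.
- PRP does not shift function: 23% pooled, 47% adjusted. Here the arm difference in T1GD is residual noise in the pooled model.

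The treatment term absorbs any arm difference, so the adjusted power is the same quantity in both cases; 46% and 47% differ only by simulation error.

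**The case against.** The strongest reply is that the plan asks only for a correlation and tests a null of no association. That is a marginal null, and the F test is valid for it. If PRP raises both variables, the marginal association is real and rejecting is correct. This stands. A reader might infer from the table that the Aim 3 test has an inflated type I error; the documents do not support that, because the rates exceed 1.25% only against a within-arm null that the plan never states. Nor does the plan say that T1GD will be presented as a marker or surrogate of function.

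The size is also conditional. It needs the full 1.7 SD effect on T1GD, an effect on function whose size appears nowhere, and zero within-arm association. It is small when the functional effect is near 0.3 SD, and it shrinks if many patients have non-contrast MRI.

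Finally, adjustment is not free. If the functional benefit runs through cartilage, the treatment term removes genuine between-arm signal, and power falls as shown above. That argues against dropping the pooled test outright. It does not argue against fitting the adjusted model, which is the one that speaks to association within arms and which gains power if PRP leaves function unchanged.

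**Conclusion.** The concern holds as a limit on interpretation. As planned, Aim 3 cannot separate imaging that tracks function within arms from two arms that differ on both measures, and the second is what the trial's own hypothesis would produce.

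The size depends on assumed functional effects. At the planned sample sizes it runs from negligible (about 2% at 0.3 SD) to substantial (20% to 26% at 1.5 SD); with few dGEMRIC patients it is modest throughout.

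The association at issue is within arms. Each patient gives one 6-month pair per model, so nothing can be said about association within patients. Aim 3 is not the primary endpoint, and the point touches neither the efficacy comparison nor safety. It merits a change because the remedy is small.

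**What to change.** Add treatment group to each of the four Aim 3 models. Report the treatment-adjusted slope with its 95% confidence interval beside the pooled association, and state that the pooled figure includes differences between arms. Conclude that imaging tracks function only if the adjusted slope supports it.

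The change is a line or two in the analysis plan and needs no new data. The Randomization section has assignment recorded as 1 or 2 in the datasets, so the statistician can fit the term without learning which arm is which.

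The cost is one residual degree of freedom (21 to 20 with 24 patients: 24 less intercept, score and age, then less treatment), and lower power for the adjusted slope if the functional benefit runs through cartilage. The adjusted slope also answers only the within-arm question, which is why the pooled estimate should stay in the report.

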### **Power Analysis**

We conducted a power analysis for Aim 1, the primary endpoint of the study. The maximum sample size for the proposed trial is fixed at 12 patients per arm (24 participants total). The sample size is limited due to costs associated with dGEMRIC.

We calculated power for the test of no difference in T1GD between the treatment groups. We assumed a standard deviation of 50 ms for T1GD values, and a correlation of 0.2 between the baseline MRI and the 12-month T1GD measurements. Estimates were based on T1GD values reported by Neuman et al[42]. We expect T1GD values to be 85 ms higher in the injection group when compared to conservative therapy at the 6 month time point with no difference at baseline. We calculated power for 10, 11, or 12 participants per arm. Power was calculated using GLIMMPSE version 2.0.1.[43]

To detect a mean difference of 85 ms in T1GD between the treatment groups, power will be 0.93 with a Type I error rate of 0.05, for 12 participants per treatment group. To ensure a conclusive study, we will target an effective sample size of 10 participants per group. Over the 12 months, we expect to lose up to two participants per treatment group. To account for the attrition, we have set an enrollment goal of 24 participants, or 12 participants per treatment group.

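### The only power figure for Aim 1 (0.93) is stated at alpha 0.05 with 12 per arm; none is given at the plan's own alpha of 0.017 with its target of 10 per arm, and the test behind it is not pinned down.

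*Combined protocol and SAP*

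**What the plan says.** The Power Analysis section calls Aim 1 the primary endpoint and gives one result: "power will be 0.93 with a Type I error rate of 0.05, for 12 participants per treatment group". The tested hypothesis is described only in words: "We calculated power for the test of no difference in T1GD between the treatment groups". The inputs are an SD of 50 ms, a correlation of 0.2 between baseline and follow-up (labelled 12-month), a group difference of 85 ms at 6 months and none at baseline. The section also says "We calculated power for 10, 11, or 12 participants per arm", but it prints only the result for 12. It then says "we will target an effective sample size of 10 participants per group", allowing for a loss of up to two per arm over 12 months, and "The maximum sample size for the proposed trial is fixed at 12 patients per arm".

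The Aim 1 analysis section sets the error rate: "Hypothesis tests will be performed at the Bonferroni corrected alpha of" 0.05/3 = 0.017. It lists the tests in order: "We will test the null hypothesis of no time by treatment by weight bearing surface by affected side interaction", and then "Given a non-significant interaction, we will test the main effects of time and treatment". The section on the research MRI using dGEMRIC takes four T1GD values per participant at each of the two scans.

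**The concern.** The figure of 0.93 uses neither the alpha at which Aim 1 will be tested nor the number of participants the plan expects to analyse. Both differences lower power. The printed result is also for the largest of the three sample sizes that were run.

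The test is not fixed either. A treatment main effect does appear in the Aim 1 analysis as a step-down test, but a pattern of 0 ms at baseline and 85 ms at 6 months does not map clearly onto it. The same inputs give quite different power for a 6-month comparison, a change from baseline, or an average over visits.

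This is the trial's only power statement, and it reads as a 7% chance of missing an 85 ms effect. It therefore governs how a non-significant Aim 1 result will be read. The planned interim power analysis after six participants also needs a fixed test and a fixed alpha.

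**Working it through.** **Inputs** (Power Analysis unless noted): SD 50 ms; correlation 0.2; difference 85 ms at 6 months and 0 at baseline; n = 12 enrolled and 10 targeted per arm; alpha 0.05 as stated in the power section, 0.017 from the Aim 1 analysis. Sidedness is not stated, so both are shown.

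**Method.** One-df tests use the noncentral t distribution with noncentrality d / (SD × √(2/n)) and df = 2n − 2 (2n − 3 if baseline-adjusted):

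- 6-month comparison: d = 85, SD = 50.
- Baseline-adjusted: d = 85, SD = 50 × √(1 − 0.2²) = 50 × √0.96 = 48.99.
- Change from baseline: d = 85, SD = 50 × √(2 × (1 − 0.2)) = 50 × √1.6 = 63.25.
- Average over the two visits: d = 85/2 = 42.5, SD = 50 × √((1 + 0.2)/2) = 50 × √0.6 = 38.73.

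A two-df test of both visits jointly uses the noncentral F with df 2 and 2n − 3 and noncentrality (n/2) × (85/48.99)², either as it stands or scaled by (2n − 3)/(2n − 2).

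**Step 1: try to reproduce 0.93.** Example, 6-month comparison with n = 12: noncentrality 85 / (50 × √(2/12)) = 4.16, df 22, two-sided critical value 2.07 at 0.05, power 0.978. At 0.017 the critical value is 2.58 and power is 0.933.

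| Test | 0.05, n=12 | 0.017, n=12 | 0.017, n=11 | 0.017, n=10 |
|---|---|---|---|---|
| 6-month, two-sided | 0.978 | 0.933 | 0.905 | 0.866 |
| Baseline-adjusted, two-sided | 0.982 | 0.941 | 0.915 | 0.877 |
| Change, two-sided | 0.882 | 0.755 | 0.705 | 0.648 |
| Visit average, two-sided | 0.729 | 0.551 | 0.501 | 0.450 |
| 6-month, one-sided | 0.991 | 0.966 | 0.949 | 0.925 |
| Baseline-adjusted, one-sided | 0.993 | 0.971 | 0.955 | 0.933 |
| Change, one-sided | 0.939 | 0.842 | 0.803 | 0.756 |
| Visit average, one-sided | 0.831 | 0.666 | 0.621 | 0.571 |
| Two-df, unscaled | 0.952 | 0.873 | 0.827 | 0.768 |
| Two-df, scaled | 0.942 | 0.854 | 0.803 | 0.739 |

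No two-sided one-df test at 0.05 with 12 per arm gives 0.93. The near matches with 12 per arm are:

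- at 0.05: one-sided change (0.939) and the two-df test (0.942 to 0.952);
- at 0.017: two-sided 6-month (0.933) and two-sided baseline-adjusted (0.941).

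**Step 2: move the near matches to the plan's own conditions** (0.017, 10 per arm). They become 0.756, 0.739 to 0.768, 0.866 and 0.877. The chance of missing 85 ms therefore runs from 1 − 0.877 = 0.12 to 1 − 0.739 = 0.26.

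**Step 3: a check that assumes no particular contrast.** Take 0.93 at two-sided 0.05 with 12 per arm as correct for some one-df test. The SD that gives this is 57.9 ms. With that SD, power is 0.874 with 10 per arm at 0.05, 0.835 with 12 per arm at 0.017, and 0.737 with both changes.

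**Step 4: the first-listed test.** The four-way interaction contrasts four sites at two visits. Its variance depends on the between-site correlations, which the plan does not give, so its power cannot be computed from one SD and one correlation.

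Using 0.05/3 exactly instead of 0.017 changes each figure in the table by 0.005 or less.

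**The case against.** The strongest reply is that no calculation is shown to be wrong. The two-sided 6-month comparison at 0.017 with 12 per arm gives 0.933, and it is close to the wording of the power section. On that reading 0.05 could be the family-wise rate that the Bonferroni split protects, and the true figure for 10 per arm is 0.87. That reading is possible, but the text does not call 0.05 family-wise, and the stated correlation of 0.2 would go unused. Even so, the value at the target sample size remains unreported.

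It can also be said that the 26% end rests on weak candidates: nothing in the plan suggests one-sided testing, the joint two-df test is not listed for Aim 1, and its scaled form is a choice. Unscaled, the miss chance is 23%. That is fair as to those candidates, but the contrast-free check gives 0.737 without relying on any of them, provided 0.05 was the per-test alpha.

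Finally, the sample size is set by cost, the analysis will report confidence intervals, and the plan admits that its power estimates may be incorrect. This limits the consequence but does not make the statement describe the planned test. Ten per arm is itself cautious, since the loss is projected over 12 months and fewer may be lost by the 6-month MRI; the figures for 11 and 12 are given for that reason. In the other direction, participants scanned without contrast supply no T1GD, which could only lower the evaluable number.

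**Conclusion.** The concern holds. The power statement does not describe the Aim 1 test as planned, and it should be corrected. It is not established that 0.93 was miscalculated: it may be right for an unstated test, or 0.05 may be a wrong label for 0.017.

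At 0.017 with 10 per arm, power is about 0.74 to 0.77 if the 0.05 label is right, and 0.87 to 0.88 if it should read 0.017. A two-sided change-from-baseline test would have 0.65. One-sided 6-month and baseline-adjusted tests would show little or no shortfall (0.92 and 0.93), but with 12 per arm at 0.05 they give 0.99, so they do not explain the stated figure.

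These results rest on the plan's own SD, correlation and effect, on one T1GD value per participant per visit, and on a loss of two per arm. Enrolment is unaffected. What changes is how much weight a non-significant Aim 1 result can bear.

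**What to change.** In the Power Analysis section:

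1. Name the Aim 1 contrast (model term, visit and site) and its sidedness, and make it one of the tests listed in the Aim 1 analysis.
2. Replace the present sentence with the power of that contrast at 0.017 with 10 evaluable per arm, and print the results for 11 and 12 as well. If 0.93 was in fact run at 0.017, correct the 0.05 label and add the figure for 10.
3. Reconcile the 12-month label on the correlation of 0.2 with the 6-month MRI. This matters only if the chosen contrast uses the baseline value.
4. Use the same contrast and alpha in the interim power analysis.

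The cost is a rerun of the calculation and some rewording. The stated power will probably become less favourable. No extra participants are needed.

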### **9. Summarize Knowledge to be Gained**

The study is designed to objectively evaluate whether intra articular injections with autologous platelet rich plasma (PRP) will improve recovery time and cartilaginous healing in patients suffering from (stable) osteochondritis dissecans of the knee when compared with conservative therapy.

Radiation-free MRI with dGEMRIC or a non-contrast MRI will be used to assess osteochondritis dissecans healing by comparing mean T1 values obtained at the site of pathology on initial and follow up exams in comparison to mean T1 values of cartilage adjacent to the site of pathology and distant to the site of pathology on initial and follow up imaging and/or interval change in DiPaolo score with Non-contrast MRI.

The benefit of more rapid healing of osteochondritis dissecans is reduction in morbidity, as well as potentially eliminating surgical treatment. Dissemination of results will occur via publication in a peer reviewed journal in the fields of radiology, orthopedic surgery, or both.

